#### 7.4 Handling of Missing, Unused, and Spurious Data and Dropouts

Every effort will be undertaken to minimize missing data. In time-to-event outcomes drop-outs will be censored at the time of discontinuation, consistent with the Kaplan-Meier approach.

Unless otherwise specified in each objective, no statistical techniques will be used to impute missing data for continuous or categorical outcomes. If a subject's data are missing for any reason, that subject will not be included in that portion of the analysis. The number of subjects included in each analysis will be reported so that the reader can assess the potential impact of missing data.

In the case of partial dates, if only the month and year are known, the event or assessment will be analyzed as if it occurred on the 15th of that month. If only the year is known, the event or assessment will be analyzed as if it occurred on June 30th of that year. These resolutions of partial dates are subject to the restrictions that pre-procedure assessments must occur between the enrollment date and the procedure date or within the window defined in the CIP. The post-procedure events and assessments must occur no earlier than the procedure date. According to the section 6.1 of the CIP, the windows for pre-procedure assessments are:

- CMR exam (functional): within 52 weeks prior to the implant date
- Clinical evaluation: within 24 weeks prior to the implant date

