#### 7.9.1.2 Data Collection and Analysis Methods

CEC adjudicated data will be used to assess the safety endpoint. The analysis cohort will be the catheterized cohort. The endpoint will be described by using Kaplan-Meier method. The loglog transformed two-sided 95% confidence interval using the Peto standard error at 30 days will be presented. The primary safety objective will be met if the point estimate of the freedom from procedure or device-related mortality rate at 30 days post-procedure is equal to or greater than the performance target of 95%.

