#### 7.9.2.2 Data Collection and Analysis Methods

Core lab data will be used to assess the efficacy endpoint, with an exception in the case that a catheterization is performed to measure mean RVOT gradient, in which site reported data will be utilized. The analysis cohort for the primary efficacy endpoint will be the implanted > 24 hours cohort. The percentage of subjects with acceptable hemodynamic function at 6 month and a two-sided 95% Clopper-Pearson confidence interval will be provided. The primary efficacy objective will be met if the point estimate is equal to or greater than the performance target of 75%.

The efficacy endpoint will be assessed using the 6-month echo, diagnostic catheterization performed during the 6-month protocol window, and reintervention status through 6 months. If 6-month echo occurred prior to 6-month time window opening or missed, next available echo that is after the 6-month window opening will be used, unscheduled or 1-year echo, which ever came first. Tables below define success or failure for all possible scenarios. Only subjects whose procedure were 6 months prior will be included in the analysis. Modified TPV 25 subjects will be excluded from the primary analysis for PMA. The primary endpoint will be evaluated again when all subjects reach 6-month visit.

Previous Reinterventions or Diagnostic Catheterization Procedures			
	6-Month Echo Not Performed or Evaluable	6-Month Echo Acceptable Hemodynamics	6-Month Echo Unacceptable Hemodynamics
Any Harmony Reintervention Prior to 6-Month Window Closing	Fail	Fail	Fail
Diagnostic Cath Acceptable Hemodynamics Prior to 6- Month Window	Not Evaluable	Success	Fail
Diagnostic Cath Acceptable Hemodynamics During 6- Month Window	Success	Success	Success
Diagnostic Cath Unacceptable Hemodynamics Prior to 6- Month Window	Not Evaluable	Success	Fail
Diagnostic Cath Unacceptable Hemodynamics During 6- Month Window	Fail	Fail	Fail

Revision 5.1 Page 17 of 24

No Previous Reinterventions or Diagnostic Catheterization Procedures			
	6-Month Echo Not Performed or Evaluable	6-Month Echo Acceptable Hemodynamics	6-Month Echo Unacceptable Hemodynamics
Previous Echo Acceptable Hemodynamics	Not Evaluable	Success	Fail
Previous Echo Unacceptable Hemodynamics	Not Evaluable	Success	Fail

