#### 7.9.2.3 Sensitivity Analysis

For the primary efficacy endpoint, percentage of subjects with acceptable hemodynamic function composite at 6 months, the primary outcome will be calculated by excluding subjects whose 6-months echo data were not evaluable. Additionally, a sensitivity analyses will be calculated using the following criteria:

- worst-case outcome assumed all unable-to-be-assessed cases were failures
- best-case outcome assumed unable-to-be-assessed cases were successes
- last value carried forward outcome assumed all unable-to-be assessed cases were successes or failures using the last available information prior to 6-month window

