#### 7.10 Safety Evaluation

Assessment of safety is defined as assessment of:

- All procedure-related serious adverse events
- All device-related serious adverse events
- Death (all-cause, procedural, and device-related)

For assessment of safety, the CEC data will be used for analysis. The analysis cohorts are:

- All procedure-related adverse events: Catheterized cohort
- All device-related adverse events: attempted implanted cohort
- Death (all-cause, procedural, and device-related): Catheterized cohort

Adverse events will be analyzed either via survival analysis using the Kaplan-Meier method or summarized by count and percent as appropriate.

Revision 5.1

Form Medtronic

Page 18 of 24

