#### Outcome Measure #2: Device success out to 5 years

Device success is defined as:

- No device- or procedural-related mortality, with
- Original intended device in place, and
- No additional surgical or interventional procedures related to access or the device since completion of the original procedure (i.e., exit from the catheterization lab), and
- Intended performance of the device, as defined as:
  - Structural performance: No migration, embolization, detachment, major stent fracture, hemolysis, thrombosis, endocarditis, and
  - Hemodynamic performance: Relief of insufficiency (PR < moderate) without producing the opposite (mean RVOT gradient > 40 mmHg) as measured by continuous wave Doppler, and
- Absence of para-device complications, as defined by:

<sup>2 If a catheterization is performed for clinical purposes, the catheterization peak gradient measurement will supersede the continuous-wave Doppler measurement and be used to support the outcome measure.

Page 19 of 24

Form

Medtronic

Revision 5.1

- o PVL ≥ moderate, or
- o Erosion, or
- o RVOT or PA rupture

The analysis cohort for device success will be the attempted implant cohort. The endpoint will be reported as Kaplan-Meier estimate for device failure which will be the opposite of device success. The loglog transformed two-sided 95% confidence interval using the Peto standard error at 6 months (183 days), 1 year (365 days), 2 years (730 days), 3 years (1095 days), 4 years (1460 days) and 5 years (1825 days) will be presented.

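### Primary efficacy scoring drops a device- or procedure-related death before a usable 6-month echo instead of failing it, and leaves a reintervention before a late substitute echo unscored

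*SAP*

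**What the plan says.** **Decision rule.** SAP 7.9.2.2 declares the efficacy objective met if the observed success percentage in the implanted > 24 hours cohort is at least 75%. There is no hypothesis test. Two grids then assign Success, Fail or Not Evaluable according to reintervention, catheterization and 6-month echo, introduced by "Tables below define success or failure for all possible scenarios".

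**Missing echo.** With no reintervention and no in-window catheterization, a subject without an evaluable echo is Not Evaluable. Under SAP 7.9.2.3, "the primary outcome will be calculated by excluding subjects whose 6-months echo data were not evaluable". SAP 7.4 gives the same rule generally: where a subject's "data are missing for any reason, that subject will not be included in that portion of the analysis". Death is not an exception in either place.

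**Where deaths do count.** The primary safety endpoint is "freedom from procedure or device-related mortality rate at 30 days post-procedure" (SAP 7.9.1.2). SAP 7.10 lists "Death (all-cause, procedural, and device-related): Catheterized cohort". Device success (SAP 7.11, Outcome Measure #2) opens with "No device- or procedural-related mortality, with". The sensitivity analyses in 7.9.2.3 include "worst-case outcome assumed all unable-to-be-assessed cases were failures" and "best-case outcome assumed unable-to-be-assessed cases were successes".

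**Substitute echo and reintervention.** If the 6-month echo was early or missed, 7.9.2.2 takes the first later echo after the window opens, unscheduled or 1-year. The first grid fails reinterventions before the window closes, and the text considers reintervention status only through 6 months. The second grid is headed as applying to subjects with no previous reintervention. The composite in 7.9.2 requires no prior reintervention but does not say prior to what.

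**The concern.** **(a) Related death, the main point.** A reintervention before the window closes is a failure even when no echo exists. A related death with no echo is removed from the denominator. The worse device outcome therefore gets the milder score, and removing it can only raise the success rate or leave it unchanged. Beyond day 30 the primary safety endpoint does not record it either.

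**(b) Late reintervention, a secondary point.** A valve that needed reintervention after week 29 could be judged on an echo taken after that reintervention. The SAP does not settle whether this is Success, Fail or Not Evaluable.

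The stake is a met-or-missed statement that rests on a bare point estimate in about 40 subjects, where single subjects can matter. The concern does not extend to other Not Evaluable subjects or to late substitution in general.

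**Working it through.** The SAP gives no sample size calculation and no expected number of either event, so there is no plan figure to reproduce. The check traces the grids and then applies the 75% rule to assumed counts.

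**Inputs.** 6-month window, weeks 23 to 29, and 1-year window, weeks 44 to 60 (Protocol 8.1). Target 75% (SAP 7.9.2.2). 40 pivotal subjects, and 20 from the Native study for pooling, 60 in all (SAP 6). Assumed: d = 1 or 2 related deaths.

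**Tracing a related death**
- After a reintervention: Fail.
- After an in-window catheterization: Success or Fail, according to its result.
- With neither, and no usable echo: Not Evaluable, hence excluded.

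The window opens on day 23 × 7 = 161, and an echo before then is not used. A related death on days 31 to 160 (130 days) therefore falls after the safety endpoint and before any usable echo. A death from day 161 until an echo is done is treated the same way, so 130 days is the minimum exposure.

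**Effect on the verdict.** Let n be evaluable subjects plus related deaths. With d deaths excluded, the fewest successes that meet the target are x = ceil(0.75 × (n − d)). The verdict can reverse if x/n is below 75%.

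| n | d | Deaths excluded | Deaths as failures | Reversal possible |
|---|---|---|---|---|
| 40 | 1 | 30/39 = 76.9% | 30/40 = 75.0% | no |
| 39 | 1 | 29/38 = 76.3% | 29/39 = 74.4% | yes |
| 38 | 1 | 28/37 = 75.7% | 28/38 = 73.7% | yes |
| 37 | 1 | 27/36 = 75.0% | 27/37 = 73.0% | yes |
| 36 | 1 | 27/35 = 77.1% | 27/36 = 75.0% | no |
| 60 | 1 | 45/59 = 76.3% | 45/60 = 75.0% | no |
| 59 | 1 | 44/58 = 75.9% | 44/59 = 74.6% | yes |
| 56 | 1 | 42/55 = 76.4% | 42/56 = 75.0% | no |
| 40 | 2 | 29/38 = 76.3% | 29/40 = 72.5% | yes |
| 60 | 2 | 44/58 = 75.9% | 44/60 = 73.3% | yes |

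One death cannot reverse the verdict when n is a multiple of 4; otherwise it can. An n below 40 is plausible, because the cohort requires the valve to stay in for more than 24 hours and other non-evaluable subjects are dropped.

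For n = 40 and d = 2, if each of the other 38 subjects has a 75% chance of success, the binomial probability of meeting the target is 51.3% with exclusion (at least 29 of 38) and 36.5% with deaths as failures (at least 30 of 38). At 80% it is 78.5% against 65.5%.

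**Tracing a reintervention after week 29.** With a 1-year substitute echo, the time from window closing to that echo is 44 − 29 = 15 to 60 − 29 = 31 weeks. The first grid does not reach a reintervention in that period, and the second excludes the subject by its heading. The undated component in 7.9.2 can be read as failing the subject; the limit to 6 months in 7.9.2.2 can be read as ignoring the event. Scoring one such subject Success instead of Fail is worth 1/40 = 2.5 points, or 1/60 = 1.7 points pooled.

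**The case against.** The strongest reply is that a death without an echo does land in a defined cell, and that its exclusion is pre-specified. The endpoint concerns hemodynamic function, the protocol's definition has no mortality component, and mortality is the separate safety endpoint. Related deaths are also reported in the safety evaluation, as device failures and as failures in the worst-case analysis, with the number analysed stated. All of this is correct, and the death is not hidden. But none of those analyses governs the 75% decision. The best-case analysis counts the death as a success, and carrying the last value forward can do the same. SAP 7.14 has already added reintervention as a failure component that the protocol did not spell out, so hemodynamics alone no longer define success.

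On (b), the reply is that 7.9.2 refers to 7.9.2.2 for detail, where the time frame is 6 months, and that the case is nearly empty. It needs no usable echo from week 23 to the reintervention, no explant, and an available regurgitation result, although no CMR is scheduled at 1 year. The rarity stands. The ambiguity also stands, because the second grid's heading and the undated component point the other way. It can also be argued that a replaced 6-month echo still counts as unable to be assessed for the sensitivity analyses. The more natural reading is that a subject with a substitute echo has been assessed.

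A late change to primary scoring, after the pivotal implants are complete, has some cost in credibility. That is a reason to document it openly.

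**Conclusion.** The concern holds and should be fixed. Under the SAP as written, a device- or procedure-related death before a usable echo, without reintervention or in-window catheterization, is excluded from the estimate that decides the efficacy objective. On days 31 to 160 it counts against neither primary endpoint. The score for a reintervention between week 29 and a substitute echo is unresolved; Success is one possible reading, and the case should be rare.

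The numerical effect is conditional. Event counts are assumed, and a reversal needs a success count at the 75% boundary. One death is enough at n = 37, 38, 39 or 59 but not at 36, 40, 56 or 60; two are enough at 40 or 60. For (b), each affected subject is worth 2.5 points at n = 40 or 1.7 at n = 60. In (a), and in (b) if read as Success, the direction is always towards a higher rate or no change.

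**What to change.** 1. Add a row to the grids in SAP 7.9.2.2 scoring a device- or procedure-related death before the 6-month assessment as Fail. Unrelated deaths can stay Not Evaluable.
2. Reconcile 7.9.2 with 7.9.2.2: date the reintervention component to the echo actually used and add the matching row, so that an echo taken after a reintervention is never scored Success. Scoring that case Not Evaluable would also close the gap, provided the choice is written down.
3. Add a sensitivity analysis that treats substitute-echo subjects as unable to be assessed, under the existing worst-case, best-case and last-value-carried-forward rules.
4. Record the changes in SAP 7.14, since item 1 goes beyond the protocol's definition of the endpoint.

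**Cost.** SAP wording and programming; death, echo and reintervention dates are already collected. The stated rate may be slightly lower, and subjects with a substitute echo will have a longer period in which a reintervention counts against them.

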#### 7.9.2.3 Sensitivity Analysis

For the primary efficacy endpoint, percentage of subjects with acceptable hemodynamic function composite at 6 months, the primary outcome will be calculated by excluding subjects whose 6-months echo data were not evaluable. Additionally, a sensitivity analyses will be calculated using the following criteria:

- worst-case outcome assumed all unable-to-be-assessed cases were failures
- best-case outcome assumed unable-to-be-assessed cases were successes
- last value carried forward outcome assumed all unable-to-be assessed cases were successes or failures using the last available information prior to 6-month window

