### 8.6.3. Device Explant

In the event of a medically indicated explant of the Harmony TPV, the explanting physician will follow standard local explant procedures. Subjects will be followed through discharge of the explant hospitalization or until study closure, whichever occurs first. Study sites should attempt to obtain copies of autopsy reports and the death certificate in the event of a subject's death. Requirements specific to explantation at reoperation or autopsy are described in **Appendix IX: EXPLANT PROTOCOL**. The explanted Harmony TPV should be returned to Medtronic as outlined in **Section 6.6. Product Return**.

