#### 7.9.2 Primary Efficacy Endpoint

The primary efficacy endpoint is percentage of subjects with acceptable hemodynamic function composite at 6 months as defined by:

- Mean RVOT gradient as measured by continuous-wave Doppler ≤40 mmHg
  - o If a catheterization is performed for clinical purposes, the catheterization peak gradient measurement will supersede the continuous-wave Doppler measurement and be used to support the primary endpoint. Acceptable hemodynamic function as measured by catheterization will be considered to be peak gradient ≤40 mmHg.

-AND-

- Pulmonary regurgitant fraction as measured by magnetic resonance imaging <20%

  - If magnetic resonance imaging is contraindicated, a continuous-wave Doppler measurement will be used to support the primary endpoint. Acceptable hemodynamic function as measured by continuous-wave Doppler will be considered to be < moderate pulmonary regurgitation.

-AND-

No prior Harmony valve reinterventions

The primary efficacy endpoint will be calculated using Core lab data, and analysis cohort will be the implanted >24 hours cohort. Analysis method details are provided in section 7.9.2.2.

Revision 5.1

Page 16 of 24

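### SAP 7.9.2.3 ties exclusion from the primary efficacy rate to echo evaluability, but the 7.9.2.2 tables score some subjects who have no evaluable echo; the two rules must be reconciled

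*SAP*

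**What the plan says.** SAP 7.9.2 adds a third component to the efficacy composite, "No prior Harmony valve reinterventions", and refers the reader to 7.9.2.2 for the details of the method.

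SAP 7.9.2.2 scores each subject from the 6-month echo, "diagnostic catheterization performed during the 6-month protocol window, and reintervention status through 6 months". If that echo was early or missed, the "next available echo that is after the 6-month window opening will be used, unscheduled or 1-year echo, which ever came first". It then states: "Tables below define success or failure for all possible scenarios". In the column for a 6-month echo that was not done or could not be read, the cells are:

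- "Any Harmony Reintervention Prior to 6-Month Window Closing": Fail.
- Catheterization inside the 6-month window: Success if acceptable, Fail if unacceptable.
- All other rows (catheterization only before the window, or only an earlier echo): Not Evaluable.

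The objective is met if the point estimate in subjects implanted for more than 24 hours is at least 75%.

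SAP 7.9.2.3, under the sensitivity-analysis heading, says "the primary outcome will be calculated by excluding subjects whose 6-months echo data were not evaluable". It then lists worst-case, best-case and last-value analyses for cases that could not be assessed, a term it does not define.

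The general missing-data rule in SAP 7.4 reads: "If a subject's data are missing for any reason, that subject will not be included in that portion of the analysis". On explant, Protocol 8.6.3 says: "Subjects will be followed through discharge of the explant hospitalization or until study closure, whichever occurs first".

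**The concern.** The 7.9.2.3 exclusion is worded as a property of the echo. The 7.9.2.2 tables treat evaluability as a property of the outcome, decided cell by cell. The two agree for most subjects but not for those who have no evaluable echo and yet carry a score in the tables.

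The group most exposed is subjects explanted before 6 months. Their follow-up ends with the explant hospitalization, so they will ordinarily have neither a 6-month echo nor a later one to replace it. If explant counts as a reintervention, the tables score them Fail, while the literal 7.9.2.3 wording takes them out of the denominator. A reintervened subject who keeps the valve stays in follow-up and is exposed only if no qualifying echo is obtained.

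The primary criterion is a bare point estimate with no hypothesis test, so the choice of denominator feeds straight into met or not met. SAP section 8 requires the primary objective to be programmed twice, independently. Two programmers could each follow the SAP and obtain different rates.

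**Working it through.** The plan gives no sample-size calculation and no expected rate, so there is no figure of its own to reproduce. The check compares the two denominators.

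**Inputs.** N = 40 pivotal subjects (SAP section 6), taken as all implanted for more than 24 hours. Target 75% (SAP 7.9.2.2). Pooled N = 40 + 20 = 60 with the earlier study (SAP section 6). k = number of table-scored failures with no qualifying echo; the documents give no explant rate, so k is an assumption, shown from 1 to 4. All other subjects are taken as evaluable, with no catheterization-only successes unless stated.

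**Formulas.** With s successes, the table reading gives s/N and the literal reading gives s/(N − k). The smallest s that meets the target is 0.75 × denominator, rounded up: 0.75 × 40 = 30 for the table reading at any k.

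| k | Literal minimum s | Literal rate | Table rate, same s |
|---|---|---|---|
| 1 | 0.75 × 39 = 29.25, so 30 | 30/39 = 76.9% | 30/40 = 75.0% (both met) |
| 2 | 0.75 × 38 = 28.5, so 29 | 29/38 = 76.3% | 29/40 = 72.5% |
| 3 | 0.75 × 37 = 27.75, so 28 | 28/37 = 75.7% | 28/40 = 70.0% |
| 4 | 0.75 × 36 = 27 | 27/36 = 75.0% | 27/40 = 67.5% |

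The results disagree for 30 minus the literal minimum values of s: none at k = 1, one at k = 2 (s = 29), two at k = 3 (28 and 29), three at k = 4 (27 to 29). The 95% Clopper-Pearson intervals at k = 2 are 59.8% to 88.6% for 29/38 and 56.1% to 85.4% for 29/40.

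**Pooled, N = 60.** The table reading needs 45. The literal minimum is 45, 44, 43 and 42 for k = 1 to 4. At k = 2, 44/58 = 75.9% against 44/60 = 73.3%.

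**Chance of meeting the target (N = 40).** This is the binomial probability of reaching the minimum among the N − k subjects who are not such failures, for an assumed true success rate in them, literal against table:

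- 75%: 0.513 vs 0.365 at k = 2; 0.588 vs 0.168 at k = 4.
- 80%: 0.784 vs 0.655 at k = 2; 0.832 vs 0.401 at k = 4.
- 85%: 0.951 vs 0.894 at k = 2; 0.965 vs 0.710 at k = 4.

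**Opposite direction.** The literal wording also drops a subject with no echo and an acceptable in-window catheterization. With one such subject, no such failures and s = 30, the table gives 30/40 = 75.0% (met) and the literal rule (30 − 1)/(40 − 1) = 29/39 = 74.4% (not met).

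**Sensitivity analyses.** Take k = 3 and s = 28. If cases that could not be assessed are the literal exclusions, the best case is (28 + 3)/40 = 77.5%, and the worst case is 28/40 = 70.0%. If they are the Not Evaluable cells only, there are none in this example and all three analyses give 28/40 = 70.0%.

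**The case against.** There is a good case that no conflict was meant. SAP 7.9.2 sends the reader to 7.9.2.2 for method, and 7.9.2.2 describes its tables as covering every scenario. Section 7.9.2.3 is about sensitivity analysis and seems only to recap the primary rule. Its phrase for what is excluded is also the label of the unscored cells, and it does not mention echoes that were never performed, which the column header does. Reintervention status is endpoint data in its own right, so a subject with a known reintervention is not missing under 7.4 and is not naturally a case that could not be assessed.

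Most of that stands, and it makes the harmonised reading the likelier intent. It does not remove the problem. The reference in 7.9.2 is not a precedence clause. The tables score subjects but do not say what happens to the Not Evaluable ones in the rate. Section 7.9.2.3 is the only endpoint-specific text that does, and it names echo data, not the composite outcome.

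A reader might infer more: that the plan does remove early device failures, or that it drops every subject without an evaluable 6-month echo. The documents do not support either.

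- Removal of failures follows only if 7.9.2.3 overrides 7.9.2.2, and nothing says that it does.
- The replacement-echo rule keeps in subjects who have a later qualifying echo.
- The literal rule would remove some successes as well as failures.
- The tables never mention explant. That surgical explant is a reintervention is an inference, supported by Protocol 6.6, which attributes explant to reintervention or autopsy. A valve recovered at autopsy is not a reintervention and has no Fail row.

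**Conclusion.** The sentence in 7.9.2.3 is wrong as written, with moderate severity: followed literally, it contradicts scored cells in 7.9.2.2 and changes the primary rate. Which reading the sponsor would apply cannot be settled from the documents, so this is a conflict to reconcile and not an established bias.

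At N = 40 the literal reading turns not met into met only when the rate is close to 75% and at least two table-scored failures lack a qualifying echo. The shift at the threshold is then 3.8 percentage points with two (76.3% − 72.5%) and 5.7 with three (75.7% − 70.0%). With one such failure the rate moves but the result does not. A catheterization-only success would move it the other way.

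These sizes rest on an assumed number of such failures and on explant counting as reintervention. The worst-case analysis would restore these subjects as failures, but the 75% criterion is applied to the primary rate.

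**What to change.** Three edits to the SAP:

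1. In 7.9.2.3, replace the sentence with: 'The primary outcome excludes only subjects classed Not Evaluable in the 7.9.2.2 tables; subjects scored Success or Fail there stay in the numerator and denominator whether or not a 6-month echo exists.'
2. Define the cases that could not be assessed, in all three sensitivity analyses, as that same Not Evaluable set, so that a subject scored Fail stays Fail throughout.
3. State in 7.9.2.2 whether surgical explant falls under Harmony reintervention.

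This adopts the SAP's own tables and adds no new endpoint component. The cost is one SAP edit and a check of the program; the reported rate may be slightly less favourable. If the primary rate has already been calculated, the report should say which denominator was used.
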